#### 4.2. Duration of Study Period:

4.2.1. There is only a single delivery of the agent, cisplatin.

4.2.2. Primary endpoint adjudication for DLT will occur after the 2 week post-procedure evaluation and laboratory values are completed.

4.2.3. The patient will be monitored for adverse events until surgical resection or for 30 days after cisplatin delivery, whichever occurs first.

#### **4.3. Treatments and Evaluations by Visit:**

##### **4.3.1. Screening Evaluation:**

4.3.1.1. Initial evaluation performed via face-to-face visit or televideo (standard of care)

4.3.1.2. A non-contrast chest CT scan will be performed within 30 days of the screening visit.

4.3.1.3. Baseline blood draws within 14 days of bronchoscopy:

4.3.1.3.1. Samples for the following laboratory tests will be sent if not available:

4.3.1.3.1.1. Hematology Panel: WBC count, RBC count, hemoglobin, hematocrit, platelet count, differential count (neutrophils, eosinophils, basophils, monocytes, lymphocytes, other cells)

4.3.1.3.1.2. Chemistry Panel (serum or plasma): sodium, potassium, chloride, bicarbonate, glucose, creatinine, albumin (pre-op only), calcium, magnesium

4.3.1.3.1.3. Liver panel: ALT, AST, INR, alkaline phosphatase, bilirubin

##### **4.3.2. Bronchoscopic Procedure:**

4.3.2.1. Pre-procedure SARS-CoV-2 testing will be performed prior to the procedure (standard of care).

4.3.2.2. Approximately 15mL of blood for research purposes will be drawn.

4.3.2.3. A pre-operative CXR will be performed if no chest imaging (CXR, CT, PET-CT) within 7 days prior to the procedure (research).

4.3.2.4. Patients will be brought to the operating room or procedure suite. Anesthesia staff will be present to administer deep sedation to minimize cough.

4.3.2.5. Standard white light bronchoscopy will be performed. (standard of care)

4.3.2.6. The linear endobronchial ultrasound bronchoscope (EBUS) will be used to perform invasive mediastinal staging. (standard of care)

4.3.2.7. For all participants, all N2 or N3 lymph nodes greater than 5mm in short axis by ultrasound will be aspirated via EBUS-TBNA and evaluated using

ROSE. Two (2) passes with lymphocytes or up to 5 non-diagnostic passes will be considered negative (ROSE charged to research). If ROSE is positive at an N2 or N3 station no agent will be delivered and the patient will be discontinued from the study.

4.3.2.8. The clinically selected bronchoscopic procedure (e.g. EBUS bronchoscope, electromagnetic navigation, robotic platform) will be used to locate the lesion of interest. The lesion will be sampled via needle aspiration. Rapid on-site cytopathologic examination will be used to evaluate needle aspirates unless the target lesion was previously sampled and diagnosed on final pathology as NSCLC. All aspirates necessary for clinical care will be obtained first. This is usually 10-20 aspirates depending on cytopathology requirements. (standard of care)

4.3.2.9. After the confirmation of NSCLC on ROSE, the research portion of the procedure will re-start.

4.3.2.10. An additional IV will be placed by anesthesiology for blood draws (research)

4.3.2.11. Before cisplatin injection, IV ampicillin-sulbactam 3g x 1 will be administered. If the patient has a beta-lactam allergy, clindamycin 900mg will be substituted).(research)

4.3.2.12. Prior to instillation of the cisplatin, 3 needle biopsies with a 21-gauge needle will be obtained for research purposes.. (research)

4.3.2.13. The 21-gauge needle will then be re-inserted into the tumor. The stylet will be removed and a syringe containing the predefined total dose of 1mg/ml cisplatin attached.

4.3.2.14. Intraoperative cone beam CT scan will be used to verify the location. If the needle tip is not located within the lesion, the needle will be repositioned using fluoroscopy. No agent will be delivered if the needle tip is not within the lesion.

4.3.2.15. Injection will then be started. If difficulty is encountered injecting with the 21G needle a 19G needle may be substituted. The same requirements for the location of the needle (4.3.2.13) will be imposed.

4.3.2.16. Following delivery of the agent, a second cone-beam CT scan will be performed to assess for extravasation of the agent.

4.3.2.17. Serial blood draws (maximum 9) for platinum levels will be drawn after delivery of cisplatin and continuing for up to 2 hours later. Each is approximately 2mL and time stamped to allow creation of a titration curve.(research)

4.3.2.18. Research time will be recorded, beginning at completion of acquisition of all samples necessary for clinical care and stopped following delivery of the agent.

4.3.2.19. The patient will be extubated and transferred to the PACU.

4.3.2.20. A follow up CXR will be performed (standard of care)

**4.3.3. 24H Post-Bronchoscopy Evaluation**

4.3.3.1. A follow up telephone/televideo or in-person evaluation will be performed by a physician, advanced practice practitioner, or nurse and will occur within 36 hours of completion of the procedure. A standard script (Appendix) will be used to assess for AEs. (research)

4.3.3.2. Blood will be drawn for an additional platinum level for patients able to return for an in-person visit.(research)

**4.3.4. 1 Week Post-Bronchoscopy Follow Up**

4.3.4.1. Participants will undergo an evaluation by a physician or advanced practice provider between 5-9 days post-procedure. Visit will occur in-person. The only exception would be COVID related issues. In that case, telemedicine and local labs will be allowed. No phone evaluations will occur unless there is no other option. A standard script will be used to assess for AEs. (research)

4.3.4.2. A blood draw to assess for AEs will be performed between 5-9 days post-procedure.(research)

4.3.4.2.1. Samples for the following laboratory tests will be sent to UVMMC laboratories for analysis:

- 4.3.4.2.1.1. Hematology Panel
- 4.3.4.2.1.2. Chemistry Panel
- 4.3.4.2.1.3. Liver Panel

4.3.4.3. Blood will be drawn for an additional platinum level.(research)

**4.3.5. 2 Week Post-Bronchoscopy Follow Up**

4.3.5.1. Participants will undergo an evaluation by a physician or advanced practice provider between 12-16 days post-procedure. Visit will occur in-person. The only exception would be COVID related issues. In that case, telemedicine and local labs will be allowed. No phone evaluations will occur unless there is no other option. A standard script will be used to assess for AEs. (research)

4.3.5.2. A blood draw to assess for AEs will be performed between 12-16 days post-procedure.(research)

4.3.5.2.1. Samples for the following laboratory tests will be sent to UVMMC laboratories for analysis:

- 4.3.5.2.1.1. Hematology Panel
- 4.3.5.2.1.2. Chemistry Panel
- 4.3.5.2.1.3. Liver Panel

4.3.6. A Chest CT will be performed between 12 and 30 days after delivery of the cisplatin.(research)

4.3.7. Surgical Resection, if planned, will be scheduled between 14 and 30 days after delivery of the cisplatin.

4.3.7.1. Approximately 15mL of blood will be drawn for research purposes on the day of (prior to) the resection procedure.

4.3.8. Routine Cancer Care

4.3.8.1. Patients will receive additional therapy at the discretion of the multidisciplinary treatment team. This review generally occurs at the University of Vermont Lung Transdisciplinary Conference (attendance generally includes but is not limited to interventional pulmonary, pulmonary, oncology, radiation oncology, cardiothoracic surgery, pathology, and thoracic radiology).

**5. PHARMACEUTICAL INFORMATION:**

- 5.1. A list of the adverse events and potential risks associated with the investigational or commercial agents administered in this study can be found in Section 10.1.
- 5.2. Formulation of Cisplatin: Cisplatin (cis-diamminedichloroplatinum) will be purchased from Fresenius/APP Pharmaceuticals. Cisplatin is a heavy metal complex containing a central atom of platinum surrounded by two chloride atoms and two ammonia molecules in the cis position. It is a yellow to orange powder with the molecular formula PtCl2H6N2, and a molecular weight of 300.05. It is soluble in water or saline at 1 mg/mL. It has a melting point of 207°C. Cisplatin Injection is a sterile aqueous solution for intravenous use, each mL containing 1 mg cisplatin and 9 mg sodium chloride. Hydrochloric acid and/or sodium hydroxide added to adjust pH. The pH range of Cisplatin Injection is 3.8-5.9.
- 5.3. Supply of Study Medication On-Site: Fresenius/APP Cisplatin will be stocked and handled in the Research Pharmacy of the University of Vermont Medical Center. It will be clearly labeled using standard and established protocols. The cisplatin will be delivered in syringes, straight drug (1mg/ml) to the OR/procedure suite.
- 5.4. Study Drug Dispensing: Once the subject has signed the Informed Consent Form to participate in the study, the subject will be associated with the research study using the Research Flag located in the patient banner section of the EPIC. The UVMMC Investigational Drug Service is alerted a study drug order will be placed in the subject's EMR by the principal investigator or designee. A study drug order is placed in EMR

using the unique study identification number, and subject's study ID number.

5.5. **Drug Accountability:** The UVMMC Investigation Drug Service will keep an inventory of all dispensed study drug. Study drug accountability logs are maintained by the IDS. Administration of study drug is recorded in subject's EMR. Study drug not administered is returned to IDS and destroyed.

5.6. **Medication Interactions:**

5.6.1. No other investigational drugs will be allowed prior to surgical resection.

5.7. **Potential Teratogenicity:**

5.7.1. Enrolled participants will be counseled that chemotherapeutics including cisplatin could be harmful to the fetus should the patient become pregnant following administration of the drug.

## 6. **STATISTICAL CONSIDERATIONS**

6.1. Study design

6.1.1. This is a 3+3 dose escalation protocol.

6.1.2. Enrollment is staggered, and no patient will be enrolled until the prior patient has completed the 1 week assessment.

6.1.3. The Initial dose cohort will be 1/4th tumor volume.

6.1.4. The subsequent dose escalation protocol is dependent on the rate of DLT as noted in the Treatment Plan.

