## 4. **TREATMENT PLAN**

### 4.1. **Agent Administration**

4.1.1. Treatment will be administered intraprocedurally. Reported adverse events and potential risks are described in the Data and Safety Monitoring Plan. No investigational or commercial agents or therapies other than those described below may be concomitantly administered with the intent to treat the patient's malignancy.

4.1.2. The agent will be administered at 3 potential dose levels in a 3+3 design.

4.1.3. IT cisplatin 1mg/ml will be dosed with a delivered volume based on a proportion of the volume of the tumor.

4.1.4. This volumetric dosing approach is being employed to account for the dramatic tumor volume differences seen in this diameter range. Prior studies have most commonly used an empirically derived intratumoral dose of 40mg or less (although have ranged to 100mg intratumorally, Appendix B). To minimize the risk of extravasation of the agent from small tumors we have adopted a volumetric dosing strategy.

4.1.4.1. First dose cohort: The delivered quantity of cisplatin will equal one-fourth (1/4th) of the total tumor volume.

4.1.4.2. De-escalation dose cohort : The delivered quantity of cisplatin will equal one-eight (1/8th) of the total tumor volume This dose cohort will only be used if the 1/4-tumor volume dose cohort is terminated due to DLT.

4.1.4.3. Escalation dose cohort: The delivered quantity of cisplatin will equal one-half (1/2) of the total tumor volume

4.1.4.4. Lower or higher dose cohorts may be pursued if indicated based on the rate of DLT, pending formal review and approval by the appointed Data Safety Monitoring Committee of the UVM Cancer Center. This is a standard approach since the DSMC reviews all AEs and relevant data at any change in dose level (pre-specified or otherwise) before preceding to the next dose level.

4.1.5. Tumor volume will be determined using automated segmentation available in the open-source software platform (<https://chestimagingplatform.org>) and manually verified.

4.1.6. The minimum volume that is feasible to deliver is 0.5mL.

4.1.7. This leads to the following “INITIAL” *example* dosing regimen for tumors of a specified volume, beginning at 1/4th Volumetric Dosing and assuming that < 2 of the first 3 participants have a dose limiting toxicity (DLT), defined as a Grade 3 by the CTCAE v5.0:

Example Tumor Volume(mL)*	Approximate Tumor Diameter (cm)*	INITIAL		First Dose Cohort:	

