		First Dose Cohort: 1/4 Tumor Volume (mL)	Delivered Volume (mL)	IT Cisplatin	Total Cisplatin (mg)
				Not Eligible**	
1.2	1.3	0.3			
1.8	1.5	0.5		0.5	0.5
4.2	2.0	1.1		1.1	1.1
8.2	2.5	2.1		2.1	2.1
14.1	3.0	3.5		3.5	3.5
22.5	3.5	5.6		5.6	5.6
33.5	4.0	8.4		8.4	8.4
47.7	4.5	11.9		11.9	11.9
65.5	5.0	16.4		16.4	16.4

\*Calculated based on volume of a sphere  
\*\*Minimum delivery volume is 0.5mL

4.1.8. The following are *example* doses for the DE-ESCALATION cohort:

Example Tumor Volume(mL)*	Approximate Tumor Diameter (cm)*	DE-ESCALATION		 Second Dose Cohort: IT Cisplatin Delivered Volume (mL)	Total Cisplatin (mg)	
		Second Dose Cohort: 1/8 Tumor Volume(mL)	Delivered Volume (mL)			
			Not Eligible**			
1.2	1.3	0.2				
1.8	1.5	0.2		Not Eligible**		
4.2	2.0	0.5		0.5	0.5	
8.2	2.5	1.0		1.0	1.0	
14.1	3.0	1.8		1.8	1.8	
22.5	3.5	2.8		2.8	2.8	
33.5	4.0	4.2		4.2	4.2	
47.7	4.5	6.0		6.0	6.0	
65.5	5.0	8.2		8.2	8.2	

\*Calculated based on volume of a sphere  
\*\*Minimum delivery volume is 0.5mL

4.1.9. The following are *example* doses for the ESCALATION cohort:

Example Tumor Volume(mL)*	Approximate Tumor Diameter (cm)*	ESCALATION			Second Dose Cohort Total Cisplatin (mg)
		Second Dose Cohort: 1/2 Tumor Volume(mL)	Second Dose Cohort	Total Cisplatin (mg)	
1.2	1.3	0.6	0.6	0.6	0.6
1.8	1.5	0.9	0.9	0.9	0.9
4.2	2.0	2.1	2.1	2.1	2.1
8.2	2.5	4.1	4.1	4.1	4.1
14.1	3.0	7.1	7.05	7.05	
22.5	3.5	11.3	11.3	11.3	
33.5	4.0	16.8	16.8	16.8	
47.7	4.5	23.9	23.9	23.9	
65.5	5.0	32.8	32.8	32.8	

\*Calculated based on volume of a sphere

\*\*Minimum delivery volume is 0.5mL

4.1.10. Dose escalation will be performed as follows:

Number of Patients with DLT at a Given Dose Level	Escalation Decision Rule
0 out of 3	Enter 3 patients at the next escalation dose.
$\geq 2$	Dose escalation will be stopped. This dose level will be declared the maximally administered dose (highest dose administered). Three (3) additional patients will be entered at the next lowest dose level if only 3 patients were treated previously at that dose. If this is the first dose evaluated, a lower dose level will be established, in concert with DSMC, and 3 patients enrolled to that level.

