1 out of 3	
Enter at least 3 more patients at this dose level.
 
 
If 0 of these 3 patients experience DLT, proceed to the next dose level.
 
If 1 or more of this group suffer DLT, then dose escalation is stopped, and this dose is declared the maximally administered dose. Three (3) additional patients will be entered at the next lowest dose level if only 3 patients were treated previously at that dose.
 

$\leq 1$ out of 6 at highest dose level below the maximally administered dose	This will be the recommended phase 2 dose. At least 6 patients must be entered at the recommended phase 2 dose.

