7.2.6.1. Definite: AE is clearly related in time and a direct association can be demonstrated to the study intervention.

7.2.6.2. Probable: AE is reasonably related in time and is more likely explained by the study intervention than by other causes.

7.2.6.3. Possible: AE may be reasonably related in time and the AE can be explained equally well by causes other than the study intervention.

7.2.6.4. Unlikely: A potential relationship could exist with the study intervention, but the AE is most likely explained by other causes.

7.2.6.5. Unrelated:AE is clearly not related to intervention and can be fully explained by another cause. This other cause should be provided.

7.2.7. Recording/reporting of baseline AEs will begin after the subject signs consent. Subsequent AEs will be recorded following initiation of the bronchoscopic procedure.

7.2.8. Recording/reporting of AEs will end following surgical resection or 30 days after cisplatin delivery, whichever occurs first.

7.2.9. The PI will review all AEs following the 1 week follow up visit (occurs at 5-9 days performed by a physician or advanced practice provider), both to assess for unexpected and serious AEs and to ensure that dose escalation occurs consistent with the statistical plan.

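### The dose can be doubled on 1-week data, although DLT is adjudicated only after the 2-week visit

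*Combined protocol and SAP*

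**What the plan says.** Five provisions of the combined protocol and SAP bear on when a tier decision may be taken.

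- **Adjudication (4.2.2):** "Primary endpoint adjudication for DLT will occur after the 2 week post-procedure evaluation and laboratory values are completed". Section 4.3.5 places that visit and its labs at days 12-16: "A blood draw to assess for AEs will be performed between 12-16 days post-procedure".
- **Enrolment gate (6.1.2):** "Enrollment is staggered, and no patient will be enrolled until the prior patient has completed the 1 week assessment". The first patient of a new tier has no separate condition.
- **Investigator review (7.2.9):** "The PI will review all AEs following the 1 week follow up visit" (days 5-9). One stated purpose is "to ensure that dose escalation occurs consistent with the statistical plan".
- **Escalation table (4.1.10):** after 0 of 3, "Enter 3 patients at the next escalation dose". After 1 of 3 and three more patients, "If 0 of these 3 patients experience DLT, proceed to the next dose level". Neither row states a length of follow-up.
- **DSMC (4.1.4.4):** "the DSMC reviews all AEs and relevant data at any change in dose level (pre-specified or otherwise) before preceding to the next dose level". No data cut-off or minimum follow-up is given.

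**The concern.** A 3+3 rule works only if each patient counted as free of DLT has been observed for the full DLT period. Here that period ends at the 2-week adjudication, while the gate and the escalation review are tied to the 1-week visit. A 1-week stagger between patients within a tier is reasonable. The gap arises at the change of tier.

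Suppose patients 1-3 at 1/4 volume show no DLT at week 1, the next tier opens, and patient 3 then has a grade 3 event at the 2-week visit. The true count is 1 of 3, for which 4.1.10 requires at least three more patients at 1/4 volume. By then a patient with resectable disease may have received twice the volumetric dose. The late event is still recorded, so the final tabulation can be corrected, but the exposure cannot be undone. Section 4.1.10 has no rule for a DLT that emerges after the next tier has opened.

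**Working it through.** **Inputs from the protocol.** 1-week window: days 5-9 (4.3.4). 2-week window: days 12-16 (4.3.5). Maximum sample size: 6 × 2 = 12, which reproduces 6.3.2. Minimum: 10 (6.3.1). Accrual: about one year (6.3.3).

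**Assumed, because the documents give neither.** True DLT rate p (20%, 30%, 40%), and share f of DLTs first seen after the 1-week visit (0, 25%, 50%).

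**1. Timing at the fastest permitted pace.** Take dosing at enrolment and a stagger of s days. When patient 4 enters, patients 1, 2 and 3 are at days 3s, 2s and s:

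| s | Patient 1 | Patient 2 | Patient 3 |
|---|---|---|---|
| 5 | 15 | 10 | 5 |
| 7 | 21 | 14 | 7 |
| 9 | 27 | 18 | 9 |

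At this pace patient 3 is always short of day 12. Patient 2 is short of it only at s = 5. Patient 3's 2-week visit is still 12 − 9 = 3 to 16 − 5 = 11 days away.

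**2. Chance of an apparent 0 of 3.** With k patients seen only to week 1, P = (1−p)^(3−k) × (1−p(1−f))^k. At p = 0.30:

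| k | f = 0 | f = 25% | f = 50% |
|---|---|---|---|
| 1 | 0.7³ = 34.3% | 0.49 × 0.775 = 38.0% | 0.49 × 0.85 = 41.65% |
| 2 | 34.3% | 0.7 × 0.775² = 42.0% | 0.7 × 0.85² = 50.6% |

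**3. Chance of escalating over both rows of 4.1.10.** Only the last patient is immature at each decision. Let a = (1−p)²(1−p(1−f)). Then P(escalate) = a + [3p(1−p)² − (1−p)²pf] × a. The bracket is the chance of exactly one true DLT among the first three that was visible at the first decision. For p = 0.30 and f = 0.25: 0.3798 + (0.441 − 0.0368) × 0.3798 = 0.533.

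| p | f = 0 | f = 25% | f = 50% |
|---|---|---|---|
| 0.20 | 70.9% | 73.6% | 76.0% |
| 0.30 | 49.4% | 53.3% | 57.0% |
| 0.40 | 30.9% | 35.2% | 39.2% |

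**4. How often this would arise.** The mean gap between patients is m = 365/12 = 30.4 to 365/10 = 36.5 days. Assume each gap is s plus an exponential time with mean m − s.

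- P(gap < 12) = 1 − exp(−(12−s)/(m−s)). This is 1 − exp(−3/27.5) = 10.3% (s = 9, 10 patients) to 1 − exp(−7/25.4) = 24.1% (s = 5, 12 patients).
- P(gap < 14), on the same basis, is 16.6% to 29.8%.
- Two immature patients at once: 0% to 1.1%.

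These figures allow no time for the DSMC review, so they are upper bounds under this accrual assumption.

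**5. Average effect.** At p = 0.30 with one immature patient, the rise in P(apparent 0 of 3) is 3.7 points (f = 25%) to 7.35 points (f = 50%). Weighted by how often it would arise, this is 0.10 × 3.7 = 0.4 to 0.30 × 7.35 = 2.2 percentage points.

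**The case against.** The best defence is that the clauses can be read together. Section 6.1.4 makes escalation depend on the DLT rate as set out in the Treatment Plan. That section holds both the table and 4.2.2, so 0 of 3 could be taken to mean three adjudicated patients. On this view 7.2.9 is only an oversight check, and the DSMC must in any case review the data before a new level. This reading is sensible, and it may be what was intended. But no sentence states it, and 7.2.9 points the other way by tying escalation oversight to the 1-week visit. A DSMC review held on 1-week data would comply with 4.1.4.4. The investigator's quarterly review of the escalation rules (9.7-9.8) is periodic and does not gate dosing. The end-of-period AE evaluation in 6.2.1.1 does not gate it either.

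Several mitigating points stand. Expected accrual is much slower than the fastest pace, enrolment may precede dosing, and any DSMC review time narrows the gap further. Only one upward step is pre-specified. The largest planned dose is 32.8 mg, under the 40 mg ceiling, and the group's late-stage series at up to 40 mg found only nausea and vomiting (2.3). These points lower the likely harm. They do not supply the missing rule, and the protocol itself chose day 12-16 labs as part of its DLT assessment.

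**Conclusion.** The concern holds. A sequence that complies with every stated condition can dose a patient at 1/2 volume before the last 1/4-volume patient has had the 2-week evaluation.

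The statistical distortion is modest. At the fastest pace, with 25-50% of DLTs late, P(escalate) rises by about 4-8 percentage points at p = 0.30 or 0.40 and about 3-5 points at p = 0.20. At the planned accrual, the average rise in P(apparent 0 of 3) is about 0.4-2.2 points. If every DLT shows by week 1 there is no effect. The probabilities rest on assumed DLT rates, late shares and accrual gaps; the timing conflict rests on the text alone. This should be fixed because it concerns the safety of an individual patient at a dose-escalation gate and is cheap to close. It does not undermine the design as a whole.

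**What to change.** Keep the 1-week stagger within a tier, and make two changes.

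1. **4.1.10:** add that no patient is dosed at a higher tier until every patient in the deciding cohort (3 or 6) has completed the 2-week DLT adjudication of 4.2.2 and the DSMC has reviewed those data under 4.1.4.4.
2. **7.2.9:** make the 1-week review a safety check only, and place the escalation review after the 2-week visit.

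A related point can be settled in the same amendment. Surgery is allowed from day 14 (4.3.7), the 2-week window runs to day 16, and AE recording stops at surgery (4.2.3, 7.2.8). State that the 2-week evaluation and labs are completed before surgery.

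The cost is protocol wording plus about one week per tier decision (3-11 days across the visit windows), incurred only when a next patient is waiting. The sample size stays at 10-12.
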